6.3.2. Solicited Adverse Reactions

The term “Solicited Adverse Reactions” refers to selected signs and symptoms occurring after vaccination administration during a specified post-vaccination follow-up period (day of vaccination and 6 subsequent days). The solicited ARs are recorded by the subject in eDiary. The occurrence and intensity of selected signs and symptoms is actively solicited from the participant during a specified post-vaccination follow-up period (day of vaccination and 6 subsequent days), using a pre-defined checklist in the eDiary (ie, solicited ARs).

The following local ARs will be solicited: pain at injection site, erythema (redness) at injection site, swelling (hardness) at injection site, and localized axillary swelling or tenderness ipsilateral to the vaccination arm.

The following systemic ARs will be solicited: headache, fatigue, myalgia (muscle aches all over the body), arthralgia (aching in several joints), nausea/vomiting, rash, fever, and chills.

The solicited ARs will be graded based on the grading scales presented in Table 3 in the protocol, modified from the Toxicity Grading Scale for Healthy Adult and Adolescent

Volunteers Enrolled in Preventive Vaccine Clinical Trials ([DHHS 2007](#)). Investigator will assess the Grading for rash and Grade 4 events (with exception of fever). Rash will be graded as:

- Grade 0 = no rash
- Grade 1 = localized without associated symptoms
- Grade 2 = maculopapular rash covering < 50% body surface area
- Grade 3 = urticarial rash covering > 50% body surface area
- Grade 4 = generalized exfoliative, ulcerative or bullous dermatitis

If a solicited local or systemic AR continues beyond 7 days post vaccination, the participant will be prompted to capture solicited local or systemic AR in the eDiary until resolution.

All solicited ARs (local and systemic) will be considered causally related to vaccination.

All solicited ARs analyses will be based on Solicited Safety Set. All solicited ARs analyses will be provided by CMV serostatus (CMV-seropositive, CMV-seronegative and overall) and vaccination group as defined in [Section 6.1](#) for each vaccination (first, second, or third), unless otherwise specified.

The number and percentage of subjects who reported any solicited AR, any solicited local AR, and any systemic solicited AR during the 7-day follow-up period after each vaccination will be tabulated by CMV serostatus, vaccination group, and vaccination, with a two-sided 95% exact CI using the Clopper-Pearson method.

The number and percentage of subjects who reported each individual solicited local AR (has a severity grade of Grade 1 or greater) and solicited systemic AR (has a severity grade of Grade 1 or greater) during the 7-day follow-up period after each vaccination will be tabulated by CMV serostatus, vaccination group, severity grade and vaccination.

The number and percentage of subjects who reported each individual solicited AR will also be summarized by CMV serostatus, vaccination group, severity grade, day of reporting and vaccination. The number and percentage of subjects experiencing fever (a temperature greater than or equal to 38.0°C/100.4°F by the oral, axillary, or tympanic route) by severity grade and the number and percentage of subjects experiencing a fever of Grade 3 or higher temperature (a temperature greater than or equal to 39.0°C/102.1°F by the oral, axillary, or tympanic route) in cumulative half-degree (°F) increments will be provided.

The onset of individual solicited AR is defined as the time point after each vaccination at which the respective solicited AR first occurred. The number and percentage of subjects with onset of individual solicited AR will be summarized by CMV serostatus, vaccination group, study day relative to corresponding vaccination (Day 1 through Day 7) and vaccination.

The duration (days) of each solicited AR will be summarized by CMV serostatus, vaccination group and vaccination. Duration will be calculated as the end day/date of the solicited AR event – the start day/date of the solicited AR event + 1, regardless of whether it is intermittent or continued. If the solicited AR continues beyond 7 days, the consecutive days a solicited AR is reported after 7 days will be included (eg, an event that lasted 5 days in the first 7 days post vaccination and 3 consecutive days beyond 7 days post vaccination, the duration will be reported as 8 (5+3) days.).

All solicited ARs (including rash) that continue beyond 7 days post vaccination will be presented in separate data listings.

6.3.3. Clinical Laboratory Evaluations

Safety laboratory testing will include hematology (hemoglobin, platelet count, and total and differential white blood cell count), serum chemistry (liver function tests including alanine aminotransferase [ALT], alkaline phosphatase [AST], total bilirubin, and creatinine) and coagulation (partial thromboplastin time [PTT] and prothrombin time [PT]).

A pregnancy test will be performed on all female subjects of childbearing potential at Screening (serum test), before each study vaccination on Visits Day 1, Month 2, and Month 6 (urine test), and as needed at unscheduled visits (urine or serum pregnancy test based on the Investigator's discretion).

Screening only laboratory test will include CMV IgG with reflex to IgM, screening serology (hepatitis B virus surface antigen [HBsAg], hepatitis C virus antibody, human immunodeficiency virus [HIV] type 1 and 2 antibodies), and follicle-stimulating hormone (FSH) level (may be measured to confirm menopausal status at the discretion of the Investigator).

All laboratory test results will be presented in the data listings. The results that are outside the reference ranges will be flagged in the data listings. The abnormalities meeting the toxicity grading criteria (Grade 2 or higher) in any safety laboratory (hematology, serum chemistry and coagulation) will be listed separately. If a subject has a laboratory test with

Grade 2 or higher abnormality at any post vaccination visit, then all results for that subject and laboratory test will be presented in the listing.

For continuous hematology, serum chemistry, and coagulation measurements, the observed values and changes from baseline will be summarized at each scheduled visit by CMV serostatus (CMV-seropositive, CMV-seronegative and overall) and vaccination group as defined in [Section 6.1](#). Shift from baseline in the toxicity grades to the worst post-baseline result will also be summarized by CMV serostatus (CMV-seropositive, CMV-seronegative and overall) and vaccination group.

6.3.4. Vital Sign Measurements

Vital sign measurements, including systolic and diastolic blood pressures, heart rate, respiratory rate, and body temperature, will be presented in a data listing. The values meeting the toxicity grading criteria will be flagged in the data listing. The abnormalities meeting the toxicity grading criteria (Grade 2 or higher) in any vital sign measurement will be listed separately. If a subject has a vital sign result with Grade 2 or higher abnormality at any post vaccination visit, then all results of vital sign measurement for that subject will be presented in the listing.

Observed values and changes from baseline for all vital sign measurements will be summarized at each scheduled visit by CMV serostatus (CMV-seropositive, CMV-seronegative, and overall) and vaccination group as defined in [Section 6.1](#). Shift from baseline in the toxicity grades will also be summarized at each scheduled visit by CMV serostatus and vaccination group.

6.4. Immunogenicity Analysis

The analyses of immunogenicity will be based on the PP Set and will be by serostatus group (ie, CMV-seropositive and CMV-seronegative groups) and vaccination group as defined in [Section 6.1](#). If the number of participants in the FAS and PP Set differ (defined as the difference divided by the total number of participants in the PP Set) by more than 10% (for each serostatus group), supportive analyses of antibody-mediated immunogenicity may be conducted using the FAS. The supportive analysis is required if the condition is met at end of study; it is optional for the interim analyses.

The GMT will be calculated using the following formula:

$$10^{\left\{ \frac{\sum_{i=1}^n \log_{10}(t_i)}{n} \right\}}$$

where t_1, t_2, \dots, t_n are n observed immunogenicity titers.

The geometric mean ratio (GMR) measures the changes in immunogenicity titers within subjects. The GMR will be calculated using the following formula:

$$10^{\left\{ \frac{\sum_{i=1}^n \log_{10}\left(\frac{v_{ij}}{v_{ik}}\right)}{n} \right\}} = 10^{\left\{ \frac{\sum_{i=1}^n \log_{10}(v_{ij}) - \log_{10}(v_{ik})}{n} \right\}}$$

where, for n subjects, v_{ij} and v_{ik} are observed immunogenicity titers for subject i at time points j and k , $j \neq k$

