**Number of Participants:**

Approximately 452 participants will be enrolled, including 252 participants in Part 1 (approximately 180 CMV-seronegative participants and approximately 72 CMV-seropositive participants) and 200 participants in Part 2 (approximately 80 CMV-seronegative participants and approximately 120 CMV-seropositive participants).

The Sponsor may enroll up to 502 participants including 252 participants in Part 1 (approximately 180 CMV-seronegative participants and approximately 72 CMV-seropositive participants) and 250 participants in Part 2 (approximately 100 CMV-seronegative participants and approximately 150 CMV-seropositive participants).

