5.5. Per-Protocol Sets

The Per-Protocol (PP) Set for Antibody-Mediated Immunogenicity

PP Set for Antibody-Mediated Immunogenicity consist of all FAS participants who

- a) comply with the vaccination schedule,
- b) comply with the timings of immunogenicity blood sampling to have post-vaccination results available for at least one assay component corresponding to the immunogenicity analysis objective (antibody-mediated immunogenicity endpoints), and
- c) have no major protocol deviations that impact immune response during the period corresponding to the immunogenicity analysis objective (antibody-mediated immunogenicity endpoints).

Subjects who were CMV seronegative at Screening and became CMV seropositive at baseline (before or on 1st dose of study vaccination) will be excluded from the PP Set for Antibody-Mediated Immunogenicity.

The PP Set for Antibody-Mediated Immunogenicity will serve as the primary population for the analysis of antibody-mediated immunogenicity data in this study. Participants will be included in the vaccination group to which they are randomized.

PP Set for CMI

PP Set for CMI consist of all FAS for Cell-Mediated participants who

- a) comply with the 3-dose vaccination schedule,
- b) comply with the timings of immunogenicity blood sampling to have post-vaccination results available for at least one assay component corresponding to the immunogenicity analysis objective (CMI endpoints), and
- c) have no major protocol deviations that impact immune response during the period corresponding to the immunogenicity analysis objective (CMI endpoints).

Subjects who were CMV seronegative at Screening and became CMV seropositive at baseline (before or on 1st dose of study vaccination) will be excluded from the PP Set for CMI.

The PP Set for CMI will serve as the primary population for the analysis of CMI data in this study. Participants will be included in the vaccination group to which they are randomized.

6. Statistical Analysis

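### The FAS immunogenicity check is triggered over a whole serostatus group, so PP exclusions concentrated in one dose arm can escape it at the final analysis

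*SAP*

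**What the plan says.** SAP 6.4 makes the PP Set the basis for immunogenicity and says the analyses "will be by serostatus group (ie, CMV-seropositive and CMV-seronegative groups) and vaccination group". Membership of the PP Set depends on events after randomisation. Under SAP 5.5 participants must "comply with the vaccination schedule", meet the sampling times, and have no major deviation that affects immune response.

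The FAS enters only through a condition. If the two sets differ "by more than 10% (for each serostatus group), supportive analyses of antibody-mediated immunogenicity may be conducted using the FAS". The difference is "defined as the difference divided by the total number of participants in the PP Set", so the measure is (FAS − PP)/PP. The force of the rule is then stated: "The supportive analysis is required if the condition is met at end of study; it is optional for the interim analyses".

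Protocol 9.6.3 has the same 10% rule without saying that it applies by serostatus group. The SAP introduction says the SAP prevails where methods differ, so the serostatus-level trigger governs.

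Two other provisions matter. SAP 6.5 combines Parts 1 and 2 at the final analysis. The ANCOVA (SAP 6.4.2) and the MMRM (SAP 6.4.4) both use the PP Set.

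**The concern.** The check is made one level above the results. GMT, GMR, fold-rise and the ANCOVA ratios are read dose by dose, but the trigger counts exclusions over three dose arms and placebo together. Exclusions spread evenly over arms do little harm to a dose comparison; exclusions concentrated in one arm can do a good deal. A total cannot tell the two apart.

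Pooling widens the gap. Part 2 adds participants only to the selected dose and to placebo. This raises the number of exclusions allowed in the serostatus group and adds nobody to the two other dose arms.

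The documents give some reason to expect unevenness. Adverse events are a listed reason for stopping vaccination (Protocol 7.1). A study pause suspends vaccination at the affected dose level and those above it (Protocol 8.9.8). Dose levels were opened in sequence (Protocol 4.2), so disruption in calendar time, including the pandemic, may fall unequally on them.

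If one arm were thinned in this way, its primary-endpoint summaries would describe a selected subset. Nothing else in the SAP would supply the wider comparison, because the ANCOVA and the MMRM use the PP Set and the visit-window sensitivity analysis removes further data.

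**Working it through.** **Inputs**

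- Enrolment (Protocol synopsis, Number of Participants): "252 participants in Part 1 (approximately 180 CMV-seronegative participants and approximately 72 CMV-seropositive participants". Part 2 adds 80 seronegative and 120 seropositive, 200 in all. The permitted maximum has "250 participants in Part 2 (approximately 100 CMV-seronegative participants and approximately 150 CMV-seropositive participants".
- Part 1 dose levels: 24 seropositive and 60 seronegative participants each. Allocation is 3:1 throughout (Protocol 4.1).
- Assumption: the FAS equals planned enrolment. The documents give no FAS size, so a range follows below.
- Dose values are redacted. *Selected* means the dose used in Part 2; *non-selected* means the other two.

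**The plan's own figures.** 252 × 3/4 = 189 and 200 × 3/4 = 150 vaccine recipients, as stated in SAP 4.2. The detection probabilities there also reproduce: 1 − 0.98^189 = 0.978 (> 95%) and 1 − 0.98^150 = 0.952 (> 90%). This confirms the 3:1 arithmetic used next.

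**Arm sizes, Parts 1 and 2 pooled**

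| Group | Each non-selected dose | Selected dose | Placebo | Total |
|---|---|---|---|---|
| Seropositive | 24 × 3/4 = 18 | 18 + 90 = 108 | 18 + 30 = 48 | 192 |
| Seronegative | 60 × 3/4 = 45 | 45 + 60 = 105 | 45 + 20 = 65 | 260 |

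**The rule.** With F in the FAS and k excluded from PP, the analysis is not triggered while k/(F − k) ≤ 0.10, that is k ≤ F/11.

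| Setting | F | Largest k not triggering | Next k triggers | Worst case in a non-selected arm |
|---|---|---|---|---|
| Seropositive, pooled | 192 | 17 (17/175 = 9.71%) | 18/174 = 10.34% | 17/18 = 94% |
| Seronegative, pooled | 260 | 23 (23/237 = 9.70%) | 24/236 = 10.17% | 23/45 = 51% |
| Seropositive, Part 1 only | 72 | 6 (6/66 = 9.09%) | 7/65 = 10.77% | 6/18 = 33% |
| Seronegative, Part 1 only | 180 | 16 (16/164 = 9.76%) | 17/163 = 10.43% | 16/45 = 36% |
| Seropositive, maximum enrolment | 222 | 20 (20/202 = 9.90%) | 21/201 = 10.45% | all 18 |
| Seronegative, maximum enrolment | 280 | 25 (25/255 = 9.80%) | 26/254 = 10.24% | 25/45 = 56% |

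The last column puts every exclusion in the serostatus group into one arm, so it is an upper bound.

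**Other arms, pooled, same worst case.** Selected dose: 17/108 = 16% seropositive and 23/105 = 22% seronegative. Placebo: 17/48 = 35% and 23/65 = 35%.

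**FAS smaller than planned.** With the FAS at 80–95% of enrolment in every arm, the worst case is 93–100% of a non-selected seropositive arm and 50–53% of a seronegative one.

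**A less extreme case.** Six exclusions in one seropositive arm of 18 and 11 elsewhere give 17 in all, so nothing is triggered. On the SAP's own measure that arm differs by 6/12 = 50%.

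**The same 10% rule applied by arm.** In an arm of 18 it triggers at 2 exclusions (2/16 = 12.5%). In an arm of 45 it triggers at 5 (5/40 = 12.5%; 4/41 = 9.76% does not).

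**The case against.** *The worst case is remote.* It needs every exclusion in a serostatus group to fall in one arm. Several routes out of the PP Set have no evident link to dose: non-study vaccines and immune-modifying drugs (Protocol 6.5.2), and seroconversion before the first dose (SAP 5.5). Exclusions of that kind would spread over arms and use up the same allowance. This stands: the 94% and 51% are bounds, not forecasts. The case of 6 in one arm and 11 elsewhere shows that the rule is also silent well short of them.

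*Reactogenicity as the cause is not shown.* Protocol 2.3.2 describes most reactions to this vaccine as mild or moderate and short. It reports an apparent rise with dose only for the systemic reactions of a related vaccine. Uneven exclusion is plausible, and the documents go no further than that.

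*A loss of that size would be seen.* SAP 6.2.1 tabulates set membership and reasons for discontinuation by serostatus and vaccination group, and SAP 6.2.6 does so for major deviation types. That is correct. But seeing an imbalance does not call up a FAS analysis, and no table gives the reasons for PP exclusion as such.

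*The FAS would not restore the participants of most interest.* This stands in large part. Under Protocol Tables 6 and 7, those who stop after one dose are sampled on Days 1, 29, 168 and 336, and those who stop after two on Days 1, 29, 56, 84, 252 and 420. Neither group has a scheduled Month 7 or Month 18 sample. SAP Appendix B maps them to separate visits.

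*The trial is descriptive.* There is no hypothesis test, but GMTs and ratios by dose are open to selection all the same.

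**Conclusion.** The gap is real and lies in the level of the trigger. At the pooled final analysis, 17 of 192 seropositive or 23 of 260 seronegative exclusions leave the FAS analysis untriggered. In the worst case this is 94% of a non-selected seropositive dose arm or 51% of a non-selected seronegative one, given planned enrolment as the FAS and all exclusions in one arm.

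A reader might infer more than the documents support:

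- That any dose arm could all but vanish unnoticed. Only the two non-selected seropositive arms come near that, and only after pooling. On Part 1 numbers the bound is about a third of an arm in either serostatus group, and the selected dose can lose at most 16% or 22%.
- That the choice of dose is in doubt. SAP 6.5 places that choice at the Month 3 interim, on a subset of Part 1 as of 26 May 2020, before any pooling. The size of that subset is not given.
- That the FAS analysis is optional at the end. The sentence following the trigger makes it mandatory then.
- That exclusions did fall unevenly. No data in the documents show this.

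The point is worth acting on because neutralising response at each dose level is a primary objective and the remedy is cheap. It is a gap in a supportive analysis of a descriptive trial, and the remedy closes it only in part.

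**What to change.** SAP version 5.0 precedes the final database lock, so the change fits there.

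1. In SAP 6.4, drop the 10% condition for the final analysis and run the antibody analyses (GMT, GMR, fold-rise and the ANCOVA) on the FAS in every case. The alternative is to keep the 10% limit and apply it to each vaccination group within serostatus. Since it would then trigger at 2 of 18 or 5 of 45, the unconditional run is simpler.
2. Add a table of reasons for exclusion from the PP Set by serostatus and vaccination group.
3. State what the FAS run can and cannot show. It mainly restores participants with out-of-window doses or samples, a skipped second dose, or other deviations. Those who stopped vaccination early contribute only at the visits on their own schedule, so not at Month 7 or Month 18. The run does not revisit the dose selection made at the interim.

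The cost is a repeat run of tables already specified on a set already defined (SAP 5.4), plus one new table. No new data are needed.

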6.4.1. Immunogenicity Assessments

There will be two types of immunogenicity assessments:

- Antibody-mediated immunogenicity assessments include serum neutralizing anti-CMV antibodies, anti-gB IgG, and anti-Pentamer IgG.
- CMI assessments include gB-specific and Pentamer-specific CD4 and CD8 cytokine secreting T-cells as measured by ICS. Blood for CMI will be collected for a subset of up to 16 participants (approximately 8 CMV-seropositive and 8 CMV-seronegative) for each dose level. Other exploratory CMI assessments may be performed.

6.4.2. Analysis of Antibody-Mediated Immunogenicity Endpoints

For each group, the following evaluations will be performed at each time point at which blood samples are collected for antibody-mediated immunogenicity (unless otherwise specified):

- GMT of the serum anti-CMV neutralizing antibody titers against epithelial cell infection and anti-CMV neutralizing antibody titers against fibroblast infection will be provided at each time point with corresponding 95% CI. The 95% CIs will be calculated based on the t-distribution of the log-transformed values then back transformed to the original scale for presentation. GMT and corresponding 95% CI

will be plotted over time. The following descriptive statistics will be also provided at each time point: the number of subjects (n), median, minimum and maximum.

- GMRs of anti-CMV neutralizing antibody titers against epithelial cell infection and anti-CMV neutralizing antibody titers against fibroblast infection at each individual post-vaccination time point over pre-vaccination (eg, Visit Day 1 [baseline]) will be tabulated with 95% CI. The 95% CIs will be calculated based on the t distribution of the difference in the log-transformed values then back transformed to the original scale for presentation. GMR and corresponding 95% CI will be plotted over time.
- In the CMV-seronegative groups, proportion of subjects with titers above baseline GMT of all CMV-seropositive subjects at each timepoint after baseline (Day 1) will be tabulated.
- Proportion of subjects with a ≥ 2 -fold, 3-fold, and 4-fold increase in serum anti-CMV neutralizing antibody titers against epithelial cell infection and anti-CMV neutralizing antibody titers against fibroblast infection from Visit Day 1 (baseline) to post-vaccination time points will be tabulated with 2-sided 95% Clopper-Pearson CIs.
- Proportion of subjects with overall seroresponse in serum anti-CMV neutralizing antibody titers against epithelial cell infection and anti-CMV neutralizing antibody titers against fibroblast infection at each individual post vaccination time point will be tabulated with 2-sided 95% Clopper-Pearson CIs. Overall seroresponse is defined as subjects who either had an undetectable titer (LLOQ) at baseline and a $\geq 2 \times$ LLOQ titer after vaccination, or a detectable titer (\geq LLOQ) at baseline and at least a 4-fold increase of baseline titer after vaccination.
- In the CMV-seropositive groups, proportion of subjects who achieve serum anti-CMV neutralizing antibody titers against epithelial cell infection and anti-CMV antibody titers against fibroblast infection greater than the third quartile of the serum anti-CMV antibody titers overall distribution at baseline (Day 1) will be tabulated.
- Anti-CMV neutralizing antibody titers against epithelial cell infection and anti-CMV neutralizing antibody titers against fibroblast infection will be displayed using reverse cumulative curves.
- For serum anti-CMV neutralizing antibody titers against epithelial cell infection and anti-CMV neutralizing antibody titers against fibroblast infection respectively, the GMT at Month 3, Month 7, Month 12, and Month 18 for each vaccination group, and

the ratio of GMT of mRNA-1647 **CCI**, mRNA-1647 **CCI**, and mRNA-1647 **CCI** vs. Placebo respectively, will be estimated based on an analysis of covariance (ANCOVA) model that will be carried out for CMV-seropositive groups and CMV-seronegative groups separately using the PP Set. For Month 3, the dependent variable will be the nAb at Month 3 with the vaccination group as a factor and the baseline values as covariate (if applicable, ie, for CMV-seropositive groups only). The GMT and corresponding 95% CI for each vaccination group, and the ratio of GMT of mRNA-1647 **CCI**, mRNA-1647 **CCI**, and mRNA-1647 **CCI** vs. Placebo respectively, together with corresponding 95% CI will be provided. A similar model at Month 7, Month 12, and Month 18 will be carried out for those who were CMV-seronegative groups, and CMV-seropositive groups separately using the PP set.

Similar analyses will be performed for gB-binding antibodies and Pentamer-binding antibodies as measured by ELISA.

